10.3. Potential Major Protocol Violations

*Note: This is a preliminary list and the final list will be generated prior to database lock.

Category	Description of Protocol Deviation
Inclusion Criteria not met but patient randomized	Male or female not ≥ 6 to < 12 years of age at time of screening visit
Inclusion Criteria not met but patient randomized	No diagnosis of AD according to the American Academy of Dermatology consensus criteria (Eichenfield 2003) at screening visit
Inclusion Criteria not met but patient randomized	Chronic AD not diagnosed at least 1 year prior to the screening visit
Inclusion Criteria not met but patient randomized	IGA < 4 at the baseline visit
Inclusion Criteria not met but patient randomized	EASI < 21 at the baseline visit
Inclusion Criteria not met but patient randomized	BSA $< 15\%$ at the baseline visit
Inclusion Criteria not met but patient randomized	Baseline worst itch score weekly average score for maximum itch intensity < 4
Inclusion Criteria not met but patient randomized	Without documented recent history (within 6 months before the baseline visit) of inadequate response to topical AD medication(s)
Inclusion Criteria not met but patient randomized	Has not applied a stable dose of topical emollient (moisturizer) twice daily for at least 11 out of 14 doses during the 7 consecutive days immediately before the baseline visit
Inclusion Criteria not met but patient randomized	Not willing and able to comply with all clinic visits and study-related procedures
Inclusion Criteria not met but patient randomized	Patient, either alone or with help of parents/legal guardians, as appropriate, is not able to understand and complete study-related questionnaires
Inclusion Criteria not met but patient randomized	Parent or legal guardian did not provide signed informed consent. Patients have not provided separate informed assent to enroll in the study, and signed and dated either a separate informed assent form (IAF) or the informed consent form (ICF) was not signed by the parent/legal guardian (as appropriate based on local regulations and requirements).
Exclusion Criteria met but patient randomized	Participation in a prior dupilumab clinical study
Exclusion Criteria met but patient randomized	Treatment with a systemic investigational drug before the baseline visit NOTE: Treatment with a systemic investigational drug refers to treatment received in a clinical study with a drug that is not yet available on the market
Exclusion Criteria met but patient randomized	Treatment with a topical investigational drug within 2 weeks prior to the baseline visit
Exclusion Criteria met but patient randomized	Treatment with crisabarole within 2 weeks prior to the baseline visit

Exclusion Criteria met but patient randomized	History of important side effects of medium-potency topical corticosteroids (eg, intolerance to treatment, hypersensitivity reactions*, significant skin atrophy, systemic effects), as assessed by the investigator or patient's treating physician *If a patient has a history of hypersensitivity reaction to any particular TCS, and/or other ingredient in the particular TCS drug product, the patient can still be randomized if the investigator believes the patient can be safely treated during the study with a different TCS drug product that does not have cross-reactivity to the drug product that caused the hypersensitivity.
Exclusion Criteria met but patient randomized	Treatment with a TCI within 2 weeks prior to the baseline visit
Exclusion Criteria met but patient randomized	Having used any of the following treatments within 4 weeks before the baseline visit, or any condition that, in the opinion of the investigator, is likely to require such treatment(s) during the first 4 weeks of study treatment: a. Immunosuppressive/immunomodulating drugs (eg, systemic corticosteroids, cyclosporine, mycophenolate-mofetil, interferon gamma, Janus kinase inhibitors, azathioprine, methotrexate, etc) b. Phototherapy for AD
Exclusion Criteria met but patient randomized	Treatment with biologics, as follows: a. Any cell-depleting agents including but not limited to rituximab: within 6 months before the baseline visit, or until lymphocyte and CD 19+ lymphocyte count returns to normal, whichever is longer b. Other biologics: within 5 half-lives (if known) or 16 weeks before the baseline visit, whichever is longer
Exclusion Criteria met but patient randomized	Treatment with a live (attenuated) vaccine within 4 weeks before the baseline visit NOTE: For patients who have vaccination with live, attenuated vaccines planned during the course of the study (based on national vaccination schedule/local guidelines), it will be determined, after consultation with a pediatrician, whether the administration of vaccine can be postponed until after the end of study, or preponed to before the start of the study, without compromising the health of the patient: • Patients for whom administration of live (attenuated) vaccine can be safely postponed would be eligible to enroll into the study. • Patients who have their vaccination preponed can enroll in the study only after a gap of 4 weeks following administration of the vaccine.
Exclusion Criteria met but patient randomized	Planned or anticipated use of any prohibited medications and procedures during study treatment
Exclusion Criteria met but patient randomized	Body weight <15 kg at baseline – all countries except Germany Body Weight <30 kg for Germany
Exclusion Criteria met but patient randomized	Initiation of treatment of AD with prescription moisturizers or moisturizers containing additives such as ceramide, hyaluronic acid, urea, or filaggrin degradation products during the screening period (patients may continue using stable doses of such moisturizers if initiated before the screening visit)
Exclusion Criteria met but patient randomized	Regular use (more than 2 visits per week) of a tanning booth/parlor within 8 weeks of the baseline visit
Exclusion Criteria met but patient randomized	Active chronic or acute infection requiring treatment with systemic antibiotics, antivirals, antiprotozoals, or antifungals within 2 weeks before the baseline visit. NOTE: patients may be rescreened after infection resolves

Exclusion Criteria met but patient randomized	Established diagnosis of a primary immunodeficiency disorder (eg, severe combined immunodeficiency, Wiskott Aldrich Syndrome, DiGeorge Syndrome, X-linked Agammaglobulinemia, common variable immunodeficiency), or secondary immunodeficiency. Patients suspected to have immunodeficiency based on their clinical presentation (history of invasive opportunistic infections eg, tuberculosis, other mycobacterial infections, histoplasmosis, listeriosis, coccidioidomycosis, pneumocystosis, chronic mucocutaneous candidiasis, etc or otherwise recurrent infections of abnormal frequency or prolonged duration suggesting an immunocompromised status, as judged by the investigator
Exclusion Criteria met but patient randomized	History of past or current tuberculosis or other mycobacterial infection Note: Irrespective of status of treatment or infection resolution. Tuberculosis testing will be performed on a country by country basis according to local guidelines if required by regulatory authorities or ethic committees.
Exclusion Criteria met but patient randomized	Known history of human immunodeficiency virus (HIV) infection or HIV seropositivity at the screening visit
Exclusion Criteria met but patient randomized	With an established diagnosis of hepatitis B viral infection at the time of screening or is positive for hepatitis B surface antigen (HBsAg) or hepatitis B core antibody (HBcAb) at the time of screening NOTE: Patients who have gained immunity for hepatitis B virus infection after vaccination (patients who are HBsAg negative, hepatitis B surface antibody [HBsAb] positive, and HBcAb negative) are eligible for the study.
Exclusion Criteria met but patient randomized	With an established diagnosis of hepatitis C viral infection at the time of screening or is positive for hepatitis C antibody at the screening visit
Exclusion Criteria met but patient randomized	On current treatment for hepatic disease including but not limited to acute or chronic hepatitis, cirrhosis, or hepatic failure, or has evidence of liver disease as indicated by persistent (confirmed by repeated tests ≥ 2 weeks apart) elevated transaminases (alanine aminotransferase [ALT] and/or aspartate aminotransferase [AST]) more than 3 times the upper limit of normal (ULN) during the screening period
Exclusion Criteria met but patient randomized	Presence of any 1 or more of the following abnormalities in laboratory test results at screening: 
 • Platelets $\leq 100 \times 10^3/\mu\text{L}$ • Neutrophils $< 1.5 \times 10^3/\mu\text{L}$ • Creatine phosphokinase (CPK) $> 5 \times \text{ULN}$ • Serum creatinine $> 1.5 \times \text{ULN}$ NOTE: If an abnormal value is detected at screening, a repeat test should be performed to confirm the abnormality. Only if the repeat test confirms the abnormality, the patient would be categorized as a screen failure.
Exclusion Criteria met but patient randomized	Presence of skin comorbidities that may interfere with study assessments. This includes, but is not limited to, conditions like scabies, seborrheic dermatitis, cutaneous T cell lymphoma, psoriasis, etc.
Exclusion Criteria met but patient randomized	History of malignancy before the baseline visit
Exclusion Criteria met but patient randomized	Diagnosed active endoparasitic infections; suspected or high risk of endoparasitic infection, unless clinical and (if necessary) laboratory assessment have ruled out active infection before randomization

Exclusion Criteria met but patient randomized	Severe concomitant illness(es) that, in the investigator's judgment, would adversely affect the patient's participation in the study. Examples include, but are not limited to patients with short life expectancy, patients with uncontrolled diabetes (hemoglobin A1c $\geq 9\%$), patients with cardiovascular conditions (eg, Class III or IV cardiac failure according to the New York Heart Association classification), severe renal conditions (eg, patients on dialysis), hepato-biliary conditions (eg, Child-Pugh class B or C), neurological conditions (eg, demyelinating diseases), active major autoimmune diseases (eg, lupus, inflammatory bowel disease, rheumatoid arthritis, etc.), other severe endocrinological, gastrointestinal, metabolic, pulmonary, or lymphatic diseases. The specific justification for patients excluded under this criterion will be noted in study documents (chart notes, case report forms [CRF], etc).
Exclusion Criteria met but patient randomized	Any other medical or psychological condition including relevant laboratory abnormalities at screening that, in the opinion of the investigator, suggest a new and/or insufficiently understood disease, may present an unreasonable risk to the study patient as a result of his/her participation in this clinical trial, may make patient's participation unreliable, or may interfere with study assessments. The specific justification for patients excluded under this criterion will be noted in study documents (chart notes, CRF, etc.).
Exclusion Criteria met but patient randomized	Planned major surgical procedure during the patient's participation in this study
Exclusion Criteria met but patient randomized	Patient or his/her immediate family is a member of the dupilumab investigational team
Exclusion Criteria met but patient randomized	Patient is female who is pregnant, breastfeeding, or planning to become pregnant or breastfeed during the study
Exclusion Criteria met but patient randomized	Patients who are committed to an institution by virtue of an order issued either by the judicial or the administrative authorities
Exclusion Criteria met but patient randomized	
Patient is female of childbearing potential* and sexually active, who is unwilling to use highly effective methods of contraception prior to the initial dose, during the study and for at least 12 weeks after the last dose of study drug. Highly effective contraceptive measures include stable use of combined (estrogen and progestogen containing) hormonal contraception (oral, vaginal, transdermal) or progestogen-only hormonal contraception (oral, injectable, implantable) associated with inhibition of ovulation initiated 2 or more menstrual cycles prior to screening; intrauterine device (IUD); intrauterine hormone-releasing system (IUS); bilateral tubal ligation; vasectomized partner; and or sexual abstinence**.
 
* For the purpose of this study, any female who has had her first menstrual period (menarche) and is sexually active will be considered to be of childbearing potential. Female patients who are not of childbearing potential at the start of the study but have the onset of menarche during the course of the study and are sexually active will also have to follow adequate birth control methods to continue participation in the study.
 
** Sexual abstinence is considered a highly effective method only if defined as refraining from heterosexual intercourse during the entire period of risk associated with the study treatments. The reliability of sexual abstinence needs to be evaluated in relation to the duration of the clinical trial and the preferred and usual lifestyle of the patient.
 
NOTE: Periodic abstinence (eg, calendar, ovulation, symptothermal, post-ovulation methods), declaration of abstinence for the duration of a study, and withdrawal are not acceptable methods of contraception.

Visit not performed	Visit 2 not performed (TCS Standardization)
Visit not performed	Visit 3 not performed (Baseline)

Visit not performed	Visit 19 not performed (End of Treatment)
Visit not performed	Early Termination visit not performed (PD not applicable for patients who completed EOT and rolled over to OLE)
Procedure not performed	IGA not performed at Screening, Baseline/Day 1 or Visit 19/EOT
Procedure not performed	EASI not performed at Screening, Baseline/Day 1 or Visit 19/EOT
Procedure not performed	BSA not performed at Screening or Baseline/Day 1
Procedure not performed	Physical Examination not performed at Screening
Procedure not performed	Electrocardiogram not performed at Screening
Procedure not performed	Serum Pregnancy testing not performed at Screening (must check WOCB at Screening visit: if Yes, for WOCB then must have results)
Procedure not performed	Urine Pregnancy testing not performed at Baseline, Visits 5, 7, 11, 15, 22/EOS or ET (must check WOCB at Screening visit: if Yes, for WOCB then must have results). Major if no pregnancy performed at all. Minor if serum performed instead of urine per protocol.
Procedure not performed	HIV, HBsAg, HBsAb, HBcAb and Hepatitis C Ab not performed at Screening visit
Procedure not performed	Hematology not performed prior to treatment with study drug at Baseline/V3
Procedure not performed	Chemistry not performed prior to treatment with study drug at Baseline/V3
Procedure not performed	Medical History information not collected at Screening
Procedure not performed	Prior Atopic Dermatitis history information not collected at Screening
Procedure not performed	Ophthalmology Exam not performed during Screening period for patients with history of conjunctivitis, blepharitis, or keratitis with 12 months of screening.
Procedure not performed	Any dose missed for non safety-related reasons for patients on Q4W.
Procedure not performed	> 1 dose missed for non safety-related reasons for patients on Q2W
Dosing non compliance	Study drug given to subject without being randomized
Prohibited medications	Treatment with Live (attenuated) vaccine during the study. Examples in section 7.8.1 of the protocol
Prohibited medications	Treatment with Immunomodulating biologics during the study
Prohibited medications	Treatment with an investigational drug (other than dupilumab) during the study
Prohibited medications	Treatment with systemic nonsteroid immunosuppressant during the study. (may be used as rescue, see section 7.3 of protocol for details)
Prohibited medications	Treatment with systemic corticosteroids during the study. (may be used as rescue, see section 7.3 of protocol for details)
Prohibited medications	Treatment with crisabarole during the study.
Prohibited medications	Treatment with TCI Note: The use of TCI is prohibited during the 2-week standardization period leading up to the baseline visit, and the treatment and follow-up periods
Prohibited medications	Treatment with high-potency or very high potency TCS, (high potency TCS may be used as rescue, see Section 7.3 for details)
Prohibited medications	Initiation of treatment of AD with prescription moisturizers

Other: Safety monitoring after study drug	Pregnancy has not been reported to sponsor per protocol requirements
Other: Laboratory	Expired lab kits used
Other: Laboratory	Pregnancy test; HIV; HBsAg; HBsAb; Hep C lab results unable to be analyzed to determine eligibility prior to treatment with study drug at Baseline/V3
Other: Laboratory	Hematology or Chemistry lab samples were unable to be analyzed to determine eligibility prior to treatment with study drug at Baseline/V3
Other: AESI	AESI not reported within protocol defined window
Other: SAE	SAE not reported within protocol defined window

10.4. Criteria for Treatment-Emergent Potentially Clinical Significant Value for Pediatric Patients (≥ 6 to < 11 years old)

Parameter	Treatment Emergent PCSV ¹	Comments
Clinical Chemistry		
ALT	≥ 3 and < 5 ULN and baseline < 3 ULN ≥ 5 and < 10 ULN and baseline < 5 ULN ≥ 10 and < 20 ULN and baseline < 10 ULN ≥ 20 ULN and baseline < 20 ULN	Enzyme activity must be expressed in ULN, not in IU/L. Concept paper on DILI – FDA draft Guidance Oct 2007. Each category is calculated independently.
AST	≥ 3 and < 5 ULN and baseline < 3 ULN ≥ 5 and < 10 ULN and baseline < 5 ULN ≥ 10 and < 20 ULN and baseline < 10 ULN ≥ 20 ULN and baseline < 20 ULN	Enzyme activity must be expressed in ULN, not in IU/L. Concept paper on DILI – FDA draft Guidance Oct 2007. Each category is calculated independently.
Alkaline Phosphatase	≥ 1.5 ULN and baseline < 1.5 ULN	Enzyme activity must be expressed in ULN, not in IU/L. Concept paper on DILI – FDA draft Guidance Oct 2007.
Total Bilirubin	≥ 1.3 ULN and baseline < 1.3 ULN	Must be expressed in ULN, not in $\mu\text{mol/L}$ or mg/L . Based on normal range: < 1 mg/dL , $\text{CF} = \text{mg} \times 1.7 = \mu\text{mol}$ Concept paper on DILI – FDA draft Guidance Oct 2007.
Conjugated Bilirubin	(Direct Bilirubin $> 35\%$ Total Bilirubin and Total Bilirubin ≥ 1.3 ULN)	Conjugated bilirubin will be measured when the total bilirubin is above the ULN Based on normal range: 0 to 0.4 mg/dL
ALT and Total Bilirubin	(ALT ≥ 3 ULN and TBILI ≥ 2 ULN) and baseline (ALT < 3 ULN and TBILI < 2 ULN)	Concept paper on DILI – FDA draft Guidance Oct 2007.
CPK	≥ 3 ULN and baseline < 3 ULN	FDA Feb 2005. Am J Cardiol April 2006.

¹ The ULN is based upon central lab reference ranges. The reference range might be different for different age-groups. For the purpose of this study in a particular patient the reference range based upon age at baseline will be used as reference throughout the study for determining PCSVs

Parameter	Treatment Emergent PCSV ¹	Comments
Creatinine	$\geq 90 \mu\text{mol/L}$ and baseline $< 90 \mu\text{mol/L}$ (or ≥ 1.1 mg/dL and baseline < 1.1 mg/dL) $\geq 30\%$ change from baseline	Benichou C., 1994 Two independent criteria
Uric Acid		
Hyperuricemia	> 8.0 mg/dL and < 8.0 mg/dl at baseline (or > 476 $\mu\text{mol/L}$ and < 476 $\mu\text{mol/L}$ at baseline	
Hypouricemia	≤ 2 mg/dL and > 2 mg/dL at baseline (or ≤ 119 $\mu\text{mol/L}$ and baseline > 119 $\mu\text{mol/L}$)	
Blood Urea Nitrogen	≥ 20 mg/dL and < 20 mg/dL at baseline (or ≥ 7.14 mmol/L and < 7.14 mmol/L at baseline)	
Chloride		Two independent criteria
Hypochloremia	< 80 mmol/L and baseline ≥ 80 mmol/L	Reference ranges are same in adolescents (12-17 yrs. old) and adults
Hyperchloremia	≥ 115 mmol/L and baseline < 115 mmol/L	
Sodium		Two independent criteria
Hyponatremia	< 129 mmol/L and baseline ≥ 129 mmol/L	Reference ranges are similar in adolescents (12-17 yrs. old) and adults
Hypernatremia	≥ 150 mmol/L and baseline < 150 mmol/L	
Potassium		FDA Feb 2005.
Hypokalemia	≤ 3.5 mmol/L and baseline > 3.5 mmol/L	Two independent criteria
Hyperkalemia	≥ 5.5 mmol/L and baseline < 5.5 mmol/L	Reference ranges are similar in adolescents (12-17 yrs. old) and adults
Calcium total	< 2 mmol/L and baseline ≥ 2 mmol/L (or ≤ 8 mg/dL and baseline > 8 mg/dL) ≥ 2.9 mmol/L and baseline < 2.9 mmol/L (or ≥ 11.6 mg/dL and baseline < 11.6 mg/dL)	
LDL Cholesterol	≥ 4.91 mmol/L and < 4.91 mmol/L at baseline (≥ 190 mg/dl and < 190 mg/dl at baseline)	Threshold for therapeutic intervention with pharmacotherapy in children (Expert Panel on Integrated Guidelines for Cardiovascular Health and Risk Reduction in Children and Adolescents; 2011).
Total cholesterol	≥ 6.20 mmol/L and < 6.20 mmol/L at baseline (or ≥ 240 mg/dL and < 240 mg/dL at baseline)	

Parameter	Treatment Emergent PCSV ¹	Comments
Triglycerides	Fasting level ≥ 5.64 mmol/L and < 5.64 mmol/L at baseline (or ≥ 500 mg/dL and < 500 mg/dL at baseline)	Threshold for therapeutic intervention with pharmacotherapy in children. (Expert Panel on Integrated Guidelines for Cardiovascular Health and Risk Reduction in Children and Adolescents; 2011). CF = g x 1.14 = mmol
Glucose		
Hypoglycaemia	< 2.7 mmol/L and ≥ 2.7 mmol/L at baseline (or < 50 mg/dL and ≥ 50 mg/dL at baseline)	
Hyperglycaemia	≥ 10 mmol/L (unfasted) and < 10 mmol/L (unfasted) at baseline (or ≥ 180 mg/dl and < 180 mg/dl at baseline); ≥ 7 mmol/L (fasted) and < 7 mmol/L (fasted) at baseline (or ≥ 120 mg/dL and < 120 mg/dL at baseline)	
HbA1c	$> 6.5\%$ and $\leq 6.5\%$ at baseline	WHO 2006/2011 ADA 2003 and 2012
Albumin	≤ 25 g/L and > 25 g/L at baseline	Reference ranges are same in children (6-17 yrs. old) and adults
Hematology		
WBC	< 5.0 Giga/L and ≥ 5.0 Giga/L at baseline > 17.0 Giga/L and ≤ 17.0 Giga/L at baseline	
Lymphocytes	< 1.0 Giga/L and ≥ 1.0 Giga/L at baseline > 8.0 Giga/L and ≤ 8.0 Giga/L at baseline	
Neutrophils	< 1.2 Giga/L and ≥ 1.2 Giga/L at baseline $> \text{ULN}$ and baseline $\leq \text{ULN}$	International Consensus meeting on drug-induced blood cytopenias, 1991. FDA criteria.
Monocytes	> 0.7 Giga/L and ≤ 0.7 Giga/L at baseline	
Eosinophils	$(> 0.5$ Giga/L and $> \text{ULN}$) and $(\leq 0.5$ Giga/L or $\leq \text{ULN}$ at baseline)	Harrison- Principles of internal Medicine 17th Ed., 2008.
Hemoglobin	< 10 g/dL and > 10 g/dL at baseline (or < 100 g/L and ≥ 100 g/L at baseline) or any decrease ≥ 2 g/dL ≥ 20 g/dL and < 20 g/dL at baseline (or ≥ 200 g/L and < 200 g/L at baseline)	Two criteria are independent
Hematocrit	$< 32\%$ and $\geq 32\%$ at baseline $> 47\%$ and $\leq 47\%$ at baseline	Two Criteria are independent

Parameter	Treatment Emergent PCSV ¹	Comments
Platelets	<100 Giga/L and \geq 100 Giga/L at baseline >700 Giga/L and \leq 700 Giga/L at baseline	International Consensus meeting on drug-induced blood cytopenias, 1991. Two independent criteria
Urinalysis		
Ketonuria	Presence and absence at baseline	Semi-quantitative methods
Glycosuria	Presence and absence at baseline	Semi-quantitative methods
Microscopic Hematuria	> 5 RBCs/ HPF and \leq 5 RBCs/ HPF at baseline	Semi-quantitative methods
Proteinuria	\geq 1+ and <1 at baseline	Semi-quantitative methods, \geq 1+ means concentration \geq 30 mg/dL
Vital signs		
HR	\leq 50 bpm and decrease from baseline \geq 20 bpm >120 bpm and increase from baseline \geq 20 bpm	
SBP	\leq 80 mmHg and decrease from baseline \geq 20mmHg \geq 108 mmHg and increase from baseline \geq 20mmHg	
DBP	\leq 48 mmHg and decrease from baseline \geq 10mmHg \geq 72 mmHg and increase from baseline \geq 20mmHg	
Temperature	Rectal, ear: >100.4 °F/38.0 °C Oral: >99.5 °F/37.5 °C Axillary: >99 °F/37.2 °C	
Respiratory rate	<16 per minute and \geq 16 per minute at baseline >30 per minute and \leq 30 per minute at baseline	
Weight	\geq 5% decrease from baseline	Based on identification of trends in the child's growth with a series of visits WHO Multicentre Reference Study Group, 2006; Center for Disease Control. Growth chart 2007.
ECG		Ref.: CPMP 1997 guideline.
HR	\leq 50 bpm and decrease from baseline \geq 20 bpm \geq 120 bpm and increase from baseline \geq 20 bpm	
PR	\geq 170 ms and <170 ms at baseline	
QRS	\geq 100 ms and <100 ms at baseline	

Parameter	Treatment Emergent PCSV ¹	Comments
QTc	Absolute values (ms) Borderline: 431-450 ms and < 431ms at baseline Prolonged: >450 ms and ≤ 450 ms at baseline Additional: ≥500 ms and < 500 ms at baseline AND Increase from baseline Borderline: Increase from baseline 30-60 ms Prolonged: Increase from baseline >60 ms	Bazett's formula (measured QT interval divided by the square root of the R-R) to be applied to arrive at corrected QT value interval) To be applied to QTcF; QTc prolonged and ΔQTc>60 ms are the PCSA to be identified in individual patient listings Independent criteria

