17. Known history of human immunodeficiency virus (HIV) infection or HIV seropositivity at the screening visit
18. With an established diagnosis of hepatitis B viral infection at the time of screening or is positive for hepatitis B surface antigen (HBsAg) or hepatitis B core antibody (HBcAb) at the time of screening  
NOTE: Patients who have gained immunity for hepatitis B virus infection after vaccination (patients who are HBsAg negative, hepatitis B surface antibody [HBsAb] positive, and HBcAb negative) are eligible for the study.
19. With an established diagnosis of hepatitis C viral infection at the time of screening or is positive for hepatitis C antibody at the screening visit
20. On current treatment for hepatic disease including but not limited to acute or chronic hepatitis, cirrhosis, or hepatic failure, or has evidence of liver disease as indicated by persistent (confirmed by repeated tests  $\geq 2$  weeks apart) elevated transaminases (alanine aminotransferase [ALT] and/or aspartate aminotransferase [AST]) more than 3 times the upper limit of normal (ULN) during the screening period

21. Presence of any 1 or more of the following abnormalities in laboratory test results at screening:

- Platelets  $\leq 100 \times 10^3/\mu\text{L}$
- Neutrophils  $< 1.5 \times 10^3/\mu\text{L}$
- Creatine phosphokinase (CPK)  $> 5 \times \text{ULN}$
- Serum creatinine  $> 1.5 \times \text{ULN}$

NOTE: If an abnormal value is detected at screening, a repeat test should be performed to confirm the abnormality. Only if the repeat test confirms the abnormality, the patient would be categorized as a screen failure.

22. Presence of skin comorbidities that may interfere with study assessments. This includes, but is not limited to, conditions like scabies, seborrheic dermatitis, cutaneous T cell lymphoma, psoriasis, etc.
23. History of malignancy before the baseline visit
24. Diagnosed active endoparasitic infections; suspected or high risk of endoparasitic infection, unless clinical and (if necessary) laboratory assessment have ruled out active infection before randomization

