#### 7.4.2.1. Reasons for Permanent Discontinuation of Study Drug

Study drug dosing will be permanently discontinued in the event of:

- Anaphylactic reaction or other severe systemic reaction to dupilumab
- Diagnosis of a malignancy during study
- Evidence of pregnancy
- Any infection that is opportunistic, such as active tuberculosis and other infections whose nature or course may suggest an immuno-compromised status
- Severe laboratory abnormalities that are deemed to be related to dupilumab:
  - Neutrophil count  $\leq 0.5 \times 10^3/\mu\text{L}$
  - Platelet count  $\leq 50 \times 10^3/\mu\text{L}$
  - ALT and/or AST values greater than  $3 \times \text{ULN}$  with total bilirubin  $> 2 \times \text{ULN}$  (unless elevated bilirubin is related to confirmed Gilbert's Syndrome)
  - Confirmed AST and/or ALT  $> 5 \times \text{ULN}$  (for more than 2 weeks)
- Treatment with any prohibited concomitant medication or procedure (Section 7.8.1). NOTE: The use of TCI is prohibited during the 2-week TCS standardization period leading up the baseline visit, and the treatment and follow-up periods. The use of very-high-potency or superpotent TCS is not allowed throughout the study (as their use is not recommended in patients under 12 years of age). However, high-potency TCS can be used as rescue. In this situation, the study drug will be continued.

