5.8. Analysis of Safety Data

The summary of safety and tolerability will be performed based on SAF.

The safety analysis will be based on the reported AEs, clinical laboratory evaluations, physical examination, vital signs and 12-lead ECG.

Thresholds for treatment-emergent Potentially Clinically Significant Values (PCSVs) in laboratory variables and vital signs are defined in [Appendix 10.4](#). Treatment-emergent PCSV is any PCSV developed or worsened in severity compared to the baseline during the treatment and follow-up period.

The time interval to detect any event or abnormality is between the first injection of study medication and EOS.

Subgroups are defined by key baseline factors recorded on the CRF and listed to be considered for safety analyses:

- Age group (≥ 6 to < 9 , ≥ 9 to < 12)
- Sex (Male, Female)
- Ethnicity: Hispanic or Latino (no/yes)
- Race (White, Black, Asian, Other)
- Duration of AD (< 5 years, ≥ 5 years)
- Baseline BMI (< 20 , ≥ 20)
- Baseline weight group (< 30 kg, ≥ 30 kg)

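### The combined ALT and bilirubin row in SAP 10.4 sets too strict a baseline condition and omits AST; the creatinine change criterion in the same table states no direction

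*SAP*

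**What the plan says.** **Definition.** SAP Section 5.8 sets the general rule: "Treatment-emergent PCSV is any PCSV developed or worsened in severity compared to the baseline during the treatment and follow-up period". Section 5.8.2 reports the number and percentage of children with such values, and Section 10.4 gives the thresholds.

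**Combined liver row (SAP 10.4).** The on-treatment part is ALT at or above 3 × ULN together with total bilirubin at or above 2 × ULN. The baseline part is "and baseline (ALT < 3 ULN and TBILI < 2 ULN", in brackets. AST does not appear in this row.

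**Neighbouring rows.** ALT and AST each have a four-level row, ending with "≥ 20 ULN and baseline < 20 ULN". Total bilirubin has its own row at 1.3 × ULN, with baseline below 1.3 × ULN. The conjugated bilirubin row carries no baseline condition. The eosinophil row also has a two-part criterion, but it joins its two baseline conditions with an or.

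**Protocol.** The combined laboratory criterion in Section 7.4.2.1 begins "ALT and/or AST values greater than" 3 × ULN, with total bilirubin above 2 × ULN, "unless elevated bilirubin is related to confirmed Gilbert's Syndrome". Exclusion criterion 20 (Section 6.2.2) removes children with persistent, repeat-confirmed "elevated transaminases (alanine aminotransferase [ALT] and/or aspartate aminotransferase [AST]) more than 3 times the upper limit of normal (ULN) during the screening period". The laboratory limits in criteria 20 and 21 include none for bilirubin.

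**Creatinine row (SAP 10.4).** There are two independent criteria: reaching 90 µmol/L from a lower baseline, or a change from baseline of at least 30%. The second gives no direction.

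**The concern.** A treatment-emergent combination is one that was absent at baseline and present later. If the combination is A and B, it is absent when A is missing or B is missing. The row instead requires both to be missing. A child who starts with one component raised, and acquires the other on treatment, has newly developed the combination under Section 5.8 but can never be counted in the row.

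This is the only row in the table that looks at a transaminase and bilirubin together. Separate counts do not show that both abnormalities occurred in one child. Safety is the trial's secondary objective, so a combined count of zero should mean that no child newly reached the combination. As written, it does not.

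There is also an anomaly with SAP Section 6.3. A child with an on-treatment abnormality and no baseline value is treated as treatment-emergent, while a child with a known raised baseline bilirubin who then reaches the combination is not.

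The AST omission and the missing creatinine direction are smaller matters of alignment and clarity.

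**Working it through.** The plan gives no figure to reproduce here, so the check is of logic.

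**Step 1: baseline clause, ALT only.** Let A mean ALT ≥ 3 × ULN and B mean total bilirubin ≥ 2 × ULN. The row's on-treatment criterion is A and B. Its exact negation at baseline is: not (A and B) = (not A) or (not B). For a child with A and B both true on treatment:

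| A at baseline | B at baseline | Combination new? | Counted by SAP row |
|---|---|---|---|
| no | no | yes | yes |
| no | yes | yes | no |
| yes | no | yes | no |
| yes | yes | no | no |

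The row counts 1 of 4 states; the exact negation counts 3 of 4.

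**Step 2: adding AST.** Let S mean AST ≥ 3 × ULN. There are 2^6 = 64 combinations of A, S and B at baseline and on treatment.

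- On treatment, (A or S) and B holds in 3 states. At baseline, the negation of (A or S) and B holds in 8 − 3 = 5 states. Newly combined: 3 × 5 = 15.
- The SAP row flags 2 on-treatment states (A and B true, S either way) × 2 baseline states (A and B false, S either way) = 4, all among the 15.
- Missed: 15 − 4 = 11. Of these, 1 × 5 = 5 are AST-only on treatment, and 2 × 5 − 4 = 6 meet the ALT criterion but had a component already raised at baseline.

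These are counts of logical states, not patient frequencies. Because the 4 lie within the 15, the wider rule drops no child whom the present row counts.

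**Step 3: illustrative children** (multiples of ULN, baseline to on-treatment; the values are invented).

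| Case | ALT | AST | Bilirubin | Combined row | ALT row | AST row | Total bilirubin row |
|---|---|---|---|---|---|---|---|
| Bilirubin raised at baseline | 1 to 8 | 1 to 8 | 2.2 to 3 | no | yes | yes | no |
| ALT raised at baseline | 3.5 to 4 | 2 to 2 | 0.5 to 2.5 | no | no | no | yes |
| AST-driven | 1 to 2 | 1 to 6 | 0.5 to 2.5 | no | no | yes | yes |
| Both normal at baseline | 1 to 4 | 1 to 4 | 0.5 to 2.5 | yes | yes | yes | yes |

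All four meet the numeric part of the protocol's combined criterion on treatment. In the first case the table shows transaminase rises and no bilirubin event, unless the conjugated bilirubin row applies.

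**Step 4: who can be affected.** Exclusion 20 makes a raised baseline ALT uncommon but not impossible: it needs confirmation of persistence, while SAP Section 6.1 takes the last valid value before the first dose as baseline. For bilirubin there is no numeric limit, so this is the main route.

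**Step 5: creatinine.** From 50 to 35 µmol/L is (35 − 50)/50 = −30%. This is flagged if change means magnitude and not flagged if it means signed change. From 50 to 65 is +30%, flagged either way. Weight, heart rate, blood pressure, hemoglobin and QTc in the same table all state a direction.

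**The case against.** **Other outputs cover much of the gap.** This stands in part. An AST-driven case with normal baseline values appears in both the AST and the total bilirubin rows. A child with raised baseline bilirubin is still flagged in the ALT row, and in the conjugated bilirubin row if direct bilirubin exceeds 35% of total. SAP 5.8.2 also lists every laboratory value by patient and visit. What these outputs lack is a count of the two abnormalities together.

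**The AST omission may be deliberate.** The row does what its title says and cites outside guidance that cannot be consulted here. The protocol criterion serves another purpose: it is a discontinuation rule, applies to abnormalities judged related to dupilumab, uses strict inequalities and exempts confirmed Gilbert's Syndrome. Nothing in the SAP says the table must reproduce it. This stands, which is why the omission is a coverage mismatch only. A reader might infer that a child who meets the discontinuation rule could disappear from safety reporting. The documents do not support that: treatment discontinuations are tabulated with reasons (SAP 5.4), and the listings remain.

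**Few children would qualify.** Exclusions 25 and 26 let the investigator exclude hepato-biliary disease or relevant laboratory abnormalities. This also stands, although neither sets a bilirubin limit. Some of those left would have Gilbert's Syndrome, which a wider row would count.

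**Creatinine.** A reader might infer that the row counts falls as safety signals. The text does not establish this: on a signed reading a 30% fall is not flagged, and the row's other criterion is upward only.

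**Conclusion.** The baseline clause is stricter than the absence of the combination at baseline, and it is inconsistent with SAP 5.8 and with the way the eosinophil row is built. A child with one component already raised who first meets the combination on treatment is not counted in that row. In logical states the row covers 1 of the 3 in which the ALT and bilirubin combination is new. The documents give no frequency; the number affected is probably small, and raised baseline bilirubin is the main route.

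The absence of AST is a mismatch with the analytes in Protocol 7.4.2.1, not a logic error. The creatinine criterion is ambiguous: two programmers could produce different counts from the same data, but it has not been shown to be wrong.

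The conclusion assumes that the row is programmed literally and that Section 5.8 is meant to govern it. The row has a single level, so the finding concerns newly developed combinations and not the worsening of one already present. The tables are descriptive, and no efficacy, alpha or power figure changes.

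**What to change.** For this reporting table only, and without touching any discontinuation rule:

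- **Liver row:** ((ALT ≥ 3 ULN or AST ≥ 3 ULN) and TBILI ≥ 2 ULN) and, at baseline, ((ALT < 3 ULN and AST < 3 ULN) or TBILI < 2 ULN). Retitle the row to include AST. Add a footnote that children with Gilbert's Syndrome may be counted, and identify any who are.
- **Creatinine row:** replace the undirected change with an increase of at least 30% from baseline, in line with the row's other criterion.

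The cost is two table cells, a footnote and the matching program lines. No new data are needed, since ALT, AST, bilirubin and creatinine are all in the chemistry panel already collected.
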